1.0 INTRODUCTION

The purpose of this post-market surveillance (PMS) is to collect data on clinical and functional outcomes with the HeartMate 3™ (HM3) left ventricular assist system (LVAS) as a treatment for advanced heart failure, refractory to optimal medical management in Hong Kong and Taiwan. The PMS is being sponsored by Abbott – the manufacturer of the HM3 LVAS.

This PMS will be conducted in accordance with this PMS plan. All investigators involved in the conduct of the study will be qualified by education, training, or experience to perform their tasks and this training will be documented appropriately.

1.1 Background and Rationale

1.1.1 Background

Patients with heart failure suffer significant morbidity and mortality. Heart Failure results when the pumping efficiency of the heart is diminished to the point of lack of end-organ perfusion. Since, allogenic heart transplantation is limited by insufficient supply of donor organs, left ventricular assist devices (LVADs) have become a mainstay of advanced heart failure treatment for patients on the waiting list and those not eligible for transplantation.

The HM3 is a durable, centrifugal-flow pump that has shown to improve the clinical and functional outcomes of advanced heart failure patients.¹ The pump is approved in multiple geographies for both short- and long-term left ventricular support for New York Heart Association (NYHA) class IIIB/IV heart failure patients.^{2,3} Hemocompatibility related adverse events have been one of the main reasons for the slow adoption of LVADs for the treatment of heart failure, in spite of the improvements seen in quality-of-life (QoL) and functional outcomes. The HM3 was designed to have an improved hemocompatibility profile, with a frictionless fully magnetically levitated rotor, wider blood flow passages, and a programmed intrinsic pulse to reduce stasis.⁴

The CE Mark trial (clinicaltrials.gov identifier: NCT02170363) for the HM3 LVAD was a prospective, multicenter, single arm trial that enrolled 50 subjects at 10 sites. This was the first clinical investigation of the HM3 left ventricular assist system (LVAS). Six-month outcomes from this trial demonstrated 92% (95% confidence interval 83-97%) survival and led to the CE Mark approval of the HM3. Analysis of longer term data demonstrated a 2-year survival of $74 \pm 6\%$.^{5,6} At 2-years, QoL and functional outcomes remained significantly improved relative to baseline: the mean EQ-5D QoL scored improved from 48.2 to 70.6; 82% of the subjects were in NYHA class I/II compared to 32% at baseline; the mean 6-minute walk distance increased from 239 to 347 m. No instances of device thrombosis were observed in this cohort at 2 years.⁶ Subjects will be followed for 5 years as a condition of CE Mark approval.

After CE Mark approval, the ELEVATE (Evaluating the HeartMate 3 with Full MagLev Technology in a Post-Market Approval Setting; clinicaltrials.gov identifier: NCT02497950) registry was initiated to collect real-world data on consecutive HM3 patients at 26 centers in Europe, Israel, Singapore, and Kazakhstan. The study enrolled 463 primary implant patients, 19 pump exchange patients, and collected only outcome data on an additional 58 patients who

Post Market Surveillance Plan

were unable to provide consent due to a study outcome (n=57 death, n=1 explant). The ELEVATE trial reported, for the primary implant cohort at 2-years, actuarial survival of 83.4%, and adverse events of stroke in 10%, suspected pump thrombosis in 1.5%, and bleeding in 34%. Mean EQ-5D score increased from 35 to 67 and 6MWT distance improved from 104 to 350 m.⁷ Subjects will be followed until the last patient completes the 5 year follow-up or experiences an outcome.

The MOMENTUM 3 study (Multi-center Study of MagLev Technology in Patients Undergoing MCS Therapy with HeartMate 3: clinicaltrials.gov identifier: NCT02224755) was a prospective, randomized, multicenter, non-blinded, clinical trial that enrolled 1,028 patients at 69 sites in the US. The study randomized patients to receive either the HM3 or HMII LVAD. The study design incorporated an initial safety phase that evaluated 30 subjects at 5 sites prior to study expansion.⁸ The primary objective of the trial was to evaluate the safety and efficacy of using the HM3 LVAD in indicated patients at two timepoints: 6 months (short-term n=294) and 2 years (long-term n=366). The primary endpoint was a composite of survival free of disabling stroke or survival free of reoperation to replace or remove the device (for reasons other than recovery).⁹ The secondary endpoint, which the study was powered to assess, was freedom from pump exchange through 2-years of follow-up in the full cohort of 1,028 patients. All study endpoints were successfully met.⁹⁻¹¹ The MOMENTUM 3 trial reported the full cohort HM3 actuarial survival at 2-years as 79.0% and stroke rates of 9.9%, suspected pump thrombosis rates of 1.4%, and bleeding rates of 43.7%.¹¹ Mean EQ-5D-5L score improved from 50 to 76. Performance on the 6-minute walk test improved from 136 to 323 m, and 80% of the subjects were determined to be NYHA class I or II relative to 0% at baseline.

1.1.2 Rationale for Conducting this Post Market Surveillance Study

The objective of this PMS is to assess clinical and functional outcomes under Hong Kong and Taiwanese standard of care for advanced heart failure patients implanted with the HM3 LVAS. PMS participants will be followed until the 24 months follow-up visit or until they experience an outcome, whichever comes first.

2.0 POST MARKET SURVEILLANCE OVERVIEW

2.1 Objective

The primary objective of this prospective, post-market surveillance study is to evaluate the functional and clinical outcomes with the HM3 LVAS, in the setting of Hong Kong and Taiwanese standard of care of advanced heart failure patients implanted with this device.

Secondary objective of this PMS is to assess the adverse events occurring during the surveillance period.

Assessments will include: 6-minute walk test (6MWT), NYHA heart failure severity classification, rates of survival, transplant, pump exchange or explant, device malfunctions, reoperations, rehospitalizations and the incidence of adverse events including, but not limited to, neurological dysfunction, bleeding, infections and device thrombosis. The definitions for the adverse events are in Appendix II and are INTERMACS definitions as used in the MOMENTUM3 study.

Post Market Surveillance Plan

2.2 Device(s) Used in the Post Market Surveillance

This PMS will be assessing functional and clinical outcomes with the HM3 as a treatment for advanced heart failure in the setting of Hong Kong and Taiwan standard-of-care.

Figure 1. The HM3 Left Ventricular Assist System. It comprises of the LVAD (A) with an inflow cannula, outflow graft, modular driveline cable, power source (i.e. batteries or power module that connects to an AC outlet), and a system controller (B).

2.2.1 Indication for Use

Please refer to the country specific IFU for the local indications for use. The HeartMate 3 Left Ventricular Assist System is indicated for providing short- and long-term mechanical circulatory support (e.g. as bridge to transplant or myocardial recovery, or destination therapy) in patients with advanced refractory left ventricular heart failure.

2.2.2 Description of the Device(s) Under Investigation

The HM3 LVAS consists of a centrifugal left ventricular assist device (LVAD) with an outflow graft and modular driveline cable, a pump controller and a power source (i.e. portable Batteries, Power Module, or Mobile Power Unit). The HM3 LVAD is comprised of an Inflow Cannula, a Pump Cover, a Lower Housing, a Screw Ring to attach the Pump Cover to the Lower Housing, a Motor, the Outflow Graft, and a Pump Cable.

The HM3 LVAD has a displacement volume of 80 milliliters and weighs 200 grams. All blood contacting surfaces are composed of titanium (LVAD body and centrifugal rotor) or gelatin-impregnated woven polyester (outflow graft). The HM3 LVAD is designed to reduce adverse events associated with LVAD thrombosis. Primary design features include full magnetic

This confidential document is the property of Abbott and shall not be reproduced, distributed, disclosed or used without the express written consent of Abbott

Post Market Surveillance Plan

levitation and large flow gaps, which minimize the shear stress imparted onto the blood elements.

The HM3 Controller is an extracorporeal interface device that receives power from the Power Module, Mobile Power Unit, or portable Batteries, and appropriately delivers that power to the HM3 LVAD. It is the primary user interface and has several important functions including:

- operating condition display,
- source of audible and visible alarms,
- communication link for transferring event/period log and alarm information, and
- battery backup in the case of full power disconnection.

The HM3 LVAD and Controller are sterilized using 100% ethylene oxide. Please refer to each device's respective local IFU for additional information regarding the device used in this PMS study. Modifications made to the device or manufacturing practices in response to issues identified during the MOMENTUM 3 IDE study are described in Appendix IV.

3.0 POST MARKET SURVEILLANCE DESIGN

[figure not shown]
This prospective, single arm, post market surveillance is designed to evaluate clinical and functional outcomes with the HM3 LVAS as a treatment for advanced heart failure. The PMS will enroll approximately 30 patients, that meet the HM3 commercially approved labelling indications, from approximately 4 sites in Hong Kong and Taiwan.

3.1 Procedures and Follow-up Schedule

The PMS Design and follow-up requirements of this post market surveillance study are described below. Follow-up visits will occur at Baseline/Enrollment, HM3 Implant, 1, 3, 6, 12 and 24 months unless the subject experiences an outcome. All visits are relative to HM3 implant.

Post Market Surveillance Plan

Figure 2: Post Market Surveillance Flowchart

Post Market Surveillance Plan

3.2 Measures Taken to Avoid and Minimize Bias

Participant selection bias will be minimized by training the PMS sites to provide all patients, that meet the HM3 commercially approved labelling indications, the opportunity to participate in this PMS. A log should be maintained of any subjects that are not included in this Registry and reasons for non-inclusion.

3.3 Suspension or Early Termination of the Post Market Surveillance

While no formal statistical rule for early termination of this PMS is defined, the Sponsor reserves the right to discontinue the PMS at any stage or reduce the follow-up period with suitable written notice to the investigator.

Should the Sponsor discontinue the post market surveillance, sites will follow subjects per routine hospital practice with device-related adverse events (AEs) reported to the Sponsor as per vigilance/commercial reporting requirements. The investigator shall return all post market surveillance materials to the Sponsor and provide a written statement to the IRB (if applicable). All applicable post market surveillance documents shall be subject to the same retention policy as detailed in Section 11.5 of the PMS plan.

If the Sponsor suspends or prematurely terminates the post market surveillance at an individual site in the interest of safety, the Sponsor will inform all other Principal Investigators.

If suspension or premature termination occurs, the Principal Investigator or authorized designee will promptly inform the enrolled subjects at his/her site, and return patients to their standard medical treatment, if appropriate.

A Principal Investigator, IRB or regulatory authority may also suspend or prematurely terminate participation in the clinical investigation at the investigational site(s) for which they are responsible. The investigators will follow the requirements specified in the Clinical Trial Agreement.

If a suspended investigation is to be resumed, a prior approval should be obtained from the IRB and a notification should be sent to the regulatory bodies.

4.0 POST MARKET SURVEILLANCE OUTCOMES

The objective of this PMS is to gather clinical and functional outcomes data from a country specific patient population that meets the HM3 commercially approved labelling indications.

The primary outcomes that will be evaluated in this post market surveillance include: functional status as measured with the 6MWT, NYHA classification of heart failure severity, quality of life measured with the EQ-5D-5L questionnaire, rates of survival, transplants, pump explant or exchange, device malfunction, reoperations, rehospitalizations and incidence of adverse events. Adverse events include, but are not limited to, neurological dysfunction, bleeding, device thrombosis and infections, that meet the definitions in Appendix II; device malfunctions will be recorded under the general category of Device Deficiencies (section 7.1.3) and is further explained in Appendix II.

This confidential document is the property of Abbott and shall not be reproduced, distributed, disclosed or used without the express written consent of Abbott

Post Market Surveillance Plan

5.0 SUBJECT SELECTION AND WITHDRAWAL

5.1 Subject Population

This post market surveillance will enroll advanced heart failure patients of all genders with a planned HM3 implant, that meet the HM3 commercially approved labelling indications. Patients must provide written informed consent prior to sites conducting any investigation-specific procedures not considered standard of care.

5.2 Subject Recruitment/Screening and Informed Consent

5.2.1 Subject Recruitment and Screening

A member of the site's post market surveillance team, previously trained to the PMS plan, must evaluate patients for the PMS eligibility criteria (Section 5.3), and if applicable, will enter the patients into a site-specific recruitment log. A patient who does not satisfy all eligibility criteria prior to informed consent is considered a recruitment failure and should not be enrolled in the post market surveillance.

Sites will ask the patients meeting the eligibility criteria to sign an Informed Consent form following the established Informed Consent process (described in Section 5.2.2) if they wish to participate in the post market surveillance. Sites will enter these patients into the recruitment log.

5.2.2 Informed Consent

The Investigator or his/her authorized designee (if applicable) will conduct the Informed Consent process, as required by applicable regulations and the center's IRB. This process will include a verbal discussion with the patient on all aspects of the post market surveillance that are relevant to the patient's decision to participate, such as details of post market surveillance procedures, anticipated benefits, and potential risks of post market surveillance participation. Sites must inform patients about their right to withdraw from the post market surveillance at any time and for any reason without sanction, penalty, or loss of benefits to which the patient is otherwise entitled. Withdrawal from the post market surveillance will not jeopardize their future medical care or relationship with the investigator.

During the discussion, the Principal Investigator or his/her authorized designee will avoid any improper influence on the patient and will respect patient's legal rights. Financial incentives will not be given to patients. Patients may be compensated for time and travel directly related to the participation in the post market surveillance. The site shall provide the patient with the Informed Consent form written in a language that is understandable to the patient and that has been approved by the center's IRB. The patient shall have adequate time to review, ask questions, and consider participation. The Principal Investigator or his/her authorized designee will make efforts to ensure that the patient understands the information provided. If the patient agrees to participate, they must sign and date the Informed Consent form, along with the person obtaining the consent prior to any post market surveillance-specific procedures. The site will file the signed original in the patient's hospital or research charts and provide a copy to the patient.

Post Market Surveillance Plan

Sites should report any failure to obtain informed consent from a patient to the Sponsor within 5 working days and to the reviewing center's IRB according to the IRB's reporting requirements.

If, during the post market surveillance, new information becomes available that can significantly affect a subject's future health and medical care, the Principal Investigator or his/her authorized designee (if applicable) will provide this information to the subject. If relevant, sites will ask the subject to confirm their continuing informed consent in writing.

This PMS will not permit informed consent via legally authorized representatives. Therefore, incapacitated individuals, including the mentally handicapped or individuals without legal authority or individuals under the age of 18 or local age of legal consent, are excluded from the PMS population. Furthermore, individuals unable to read or write are excluded from the PMS population.

5.3 Eligibility Criteria

All patients at the participating sites that are determined to meet the HM3 commercially approved labelling indication and have a planned HM3 implant are eligible to participate in this PMS. Assessment for eligibility criteria is based on medical records of the site and interview with a candidate patient.

5.4 Subject Enrollment

A patient is considered enrolled in the post market surveillance from the moment the patient provides written informed consent.

5.5 Subject Withdrawal and Discontinuation

All subjects enrolled in the study shall remain in the post market surveillance until they performed the 24 month follow-up or they experience an outcome (death, transplant, HM3 explant or exchange, or withdrawal), whichever comes first; however, a subject's participation in any clinical investigation is voluntary and the subject has the right to withdraw at any time without penalty or loss of benefit. Conceivable reasons for discontinuation may include, but not be limited to, the following:

- Physician or subject voluntary withdrawal
- Subject lost-to follow-up as described below
- Non-compliance with the PMS plan
- Subject is not on primary HM3 support

Sites must notify the Sponsor of the reason(s) for subject discontinuation. Investigators must also report this to their respective IRB as defined by their institution's procedure(s).

No additional follow-up is required, or data recorded from subjects once withdrawn from the post market surveillance, except for the status (deceased/alive).

Post Market Surveillance Plan

In case of subject withdrawal of consent, the site should make attempts to schedule the subject for a final post market surveillance visit. At this final follow-up visit, the subject will undergo the following assessments:

- Adverse events since the last follow-up
- Transplant, explant/exchange or device deficiency since the last follow-up
- Subject outcomes

Lost-to-Follow-up

If the subject misses two consecutive scheduled follow-up time points and the attempts at contacting the subject detailed below are unsuccessful, then the subject is considered lost-to-follow-up. Site personnel shall make all reasonable efforts to locate and communicate with the subject (and document these efforts in the source documents), including the following, at each contact time point:

- A minimum of two telephone calls on different days over the specified follow-up windows to contact the subject should be recorded in the source documentation, including date, time and initials of site personnel trying to make contact.
- If these attempts are unsuccessful, the site should send a letter (certified if applicable) to the subject.
- If a subject misses one or more non-consecutive follow-up contact time points, it will be considered a missed visit. The subject may then return for subsequent visits. If the subject misses two consecutive time points and the above-mentioned attempts at communicating with the subject are unsuccessful, the subject will be considered lost-to-follow-up.

Note: Telephone contact with general practitioner, non-PMS cardiologist or relative without the presence of the subject or indirect documentation obtained via discharge letters will not be considered as subject contact.

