7.3 Adverse Event and Device Deficiency Reporting

7.3.1 Adverse Event Reporting

Safety surveillance and reporting starts as soon as the patient is enrolled in the post market surveillance. Safety surveillance and reporting will continue until sites perform the last follow-up visit, the subject is deceased, the subject concludes participation in the post market surveillance, or the subject withdraws from the post market surveillance. Sites will collect all adverse event data, including deaths and device deficiency data, throughout the period defined above and will report these events to the Sponsor on a CRF. Sites should update additional information regarding an adverse event on the appropriate CRF.

Unchanged, chronic, non-worsening or pre-existing conditions are not AEs and should not be reported.

The Sponsor will provide an offline form to allow the investigator to report SAEs in the event the entry cannot be made in the EDC. This does not replace the EDC reporting system. Sites must still enter all information in the EDC system as soon as feasible.

Non-cardiac related abnormal laboratory values will not be considered AEs unless:

1. the investigator determined that the value is clinically significant, OR
2. the abnormal lab value required intervention, OR
3. the abnormal lab value required subject withdrawal from the post market surveillance

This confidential document is the property of Abbott and shall not be reproduced, distributed, disclosed or used without the express written consent of Abbott

Post Market Surveillance Plan

All adverse events will be collected on each subject throughout the follow up period – until the subject reaches an outcome or withdraws or until the surveillance ends. Causes of death will be captured for all subjects who expire during follow up.

SAE Reporting

The investigator must report all SAEs to the Sponsor as soon as possible but no later than outlined below.

Clinical Site	Reporting timelines
All Sites	Sites must report SAEs to the Sponsor no later than 3 calendar days from the day the site personnel became aware of the event or as per the investigative site's local requirements, if the requirement is more stringent than those outlined.

Sites must record the date the site staff became aware that the event met the criteria of an SAE in the source document. The Investigator will further report the SAE to the local IRB according to the institution's IRB reporting requirements.

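### Section 5.5 lets a subject who still consents and is still on HM3 support be discontinued, after which non-fatal events are no longer recorded and the primary efficacy analysis censors the subject

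*Protocol*

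**What the plan says.** Protocol 5.5 sets the default that "All subjects enrolled in the study shall remain in the post market surveillance until they performed the 24 month follow-up" or have an outcome, and it counts withdrawal as an outcome. It then opens a list with "Conceivable reasons for discontinuation may include, but not be limited to, the following". The list contains voluntary withdrawal by physician or subject, loss to follow-up, "Non-compliance with the PMS plan", and no longer being on primary HM3 support. Non-compliance is not defined and has no threshold.

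The data rule that follows is: "No additional follow-up is required, or data recorded from subjects once withdrawn from the post market surveillance, except for the status (deceased/alive". No other rule is given for discontinued subjects. The final visit, which would cover adverse events, transplant, explant or exchange, and device deficiencies, has a narrower trigger: "In case of subject withdrawal of consent, the site should make attempts to schedule the subject for a final post market surveillance visit".

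Protocol 7.3.1 agrees with this. Adverse events are collected "until the subject reaches an outcome or withdraws or until the surveillance ends". In the primary efficacy analysis, Protocol 8.2.1 and SAP 2.2.3 censor subjects who withdraw at the time of withdrawal. The primary safety endpoint (Protocol 8.2.2, SAP 2.2.4) is the percent of subjects with each event and events per patient-year. Missing data are not imputed apart from the walk-test zero rule (Protocol 8.6, SAP 2.8), and the SAP body describes no sensitivity analysis.

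**The concern.** By Protocol 3.0 the surveillance "is designed to evaluate clinical and functional outcomes with the HM3 LVAS as a treatment for advanced heart failure". The device stays in place when a subject is discontinued for non-compliance or by a physician's decision, so the subject remains at risk of stroke, bleeding, infection and pump exchange. As written, none of those later events enters the study data. Vital status is kept, but because the analysis censors at withdrawal, a later death would not count in the composite either.

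Such a subject also gets less closing data collection than one who withdraws consent, since the final assessment is tied to withdrawal of consent. The loss is avoidable: Protocol 15.4 describes the study assessments as standard of care that would be done regardless, so much of the information should already be in site records. At stake is mainly the primary safety summary, and, if discontinuation is related to risk, the primary efficacy estimate as well.

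**Working it through.** **Text check.** Four rules act in sequence:

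1. 5.5 permits discontinuation without withdrawal of consent.
2. 5.5 and 7.3.1 stop event collection at withdrawal.
3. 5.5 attaches the closing assessment to withdrawal of consent only.
4. 8.2.1 and SAP 2.2.3 censor at withdrawal.

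The one route that stays open, in 7.3.2, sends device deficiencies to the sponsor's complaints database. It does not cover strokes or bleeds as such, and it lies outside the study analysis. Section 5.5 speaks of both discontinuation and withdrawal. Applying the vital-status rule to both is the natural reading, because no other rule is given.

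**Illustration.** The plan has no figure to reproduce: there is no sample size calculation and the endpoints are not powered. The inputs are:

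- From the documents: N = 30 (Protocol 5.6). Two-year HM3 incidence p is 43.7% for bleeding and 9.9% for stroke (MOMENTUM 3 full cohort, Protocol 1.1.1). The stroke figure covers all strokes, not only debilitating ones.
- Assumed: k = 1, 3 or 5 subjects discontinued, at t = 0.5 or 1 year, with hazard r = 1, 2 or 3 times that of the others. Hazards are constant and there are no other losses.

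Annual hazard h = −ln(1 − p)/2. For bleeding this is −ln(0.563)/2 = 0.287; for stroke, −ln(0.901)/2 = 0.052.

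What is recorded when collection stops at t:

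- Percent with event = [(N − k)(1 − e^(−2h)) + k(1 − e^(−rht))]/N
- Events per patient-year = h[2(N − k) + krt]/[2(N − k) + kt]
- Kaplan-Meier incidence = 1 − S(t)·e^(−h(2 − t)), with S(u) = [(N − k)e^(−hu) + ke^(−rhu)]/N

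Full collection sets t = 2.

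Bleeding, k = 3, t = 0.5, r = 1: each discontinued subject has a recorded probability of 1 − e^(−0.287 × 0.5) = 0.134. Percent recorded = (27 × 0.437 + 3 × 0.134)/30 = 12.20/30 = 40.7%, against 43.7% with full collection.

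Same case with r = 2: full = (27 × 0.437 + 3 × 0.683)/30 = 46.2%; recorded = (27 × 0.437 + 3 × 0.250)/30 = 41.8%. Events per patient-year: full = 0.287 × 66/60 = 0.316; recorded = 0.287 × 57/55.5 = 0.295.

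| Left at month 6 | Hazard ratio | % with bleeding, full → recorded | % with stroke | Bleeding events per patient-year | Kaplan-Meier bleeding |
|---|---|---|---|---|---|
| 1 of 30 | 1 | 43.7 → 42.7 | 9.9 → 9.7 | 0.287 → 0.287 | 43.7 → 43.7 |
| 1 of 30 | 3 | 45.0 → 43.4 | 10.5 → 9.8 | 0.306 → 0.292 | 45.0 → 44.2 |
| 3 of 30 | 1 | 43.7 → 40.7 | 9.9 → 9.2 | 0.287 → 0.287 | 43.7 → 43.7 |
| 3 of 30 | 2 | 46.2 → 41.8 | 10.8 → 9.4 | 0.316 → 0.295 | 46.2 → 44.5 |
| 5 of 30 | 3 | 50.1 → 42.3 | 12.7 → 9.5 | 0.383 → 0.315 | 50.1 → 46.0 |

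Leaving at month 12 gives smaller losses (3 of 30 at equal risk: 43.7 → 41.8). The percent of patients falls in every row. The other two measures move only when r differs from 1.

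**The case against.** The strongest reply is that section 5.5 does not order anyone's removal. Its list is explicitly one of conceivable reasons, under a default that subjects stay in, so removals may be few or none. Ordinary non-compliance is also handled elsewhere. For a subject with non-consecutive missed visits, the rule is "The subject may then return for subsequent visits". Two consecutive misses become loss to follow-up only after failed contact attempts. Out-of-window assessments are deviations (6.3), and deviations go on their own form (10.5). Sites must also tell the sponsor why a subject was discontinued, so removals would be visible. All of this stands and limits how often the gap would matter. None of it keeps events in the data once a discontinuation has happened.

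Four stronger readings are tempting and should be resisted.

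- **That non-compliant subjects are a higher-risk group, so the primary efficacy result is biased.** The documents say nothing about their risk. At equal risk the Kaplan-Meier estimate is unbiased, and events per patient-year lose person-time along with events. A lower event count is not by itself a biased estimate.
- **That section 5.5 contradicts itself by keeping everyone to Month 24 and then listing removal.** It does not: the same sentence counts withdrawal as an outcome that ends follow-up.
- **That the share of subjects removed measures the bias.** One to three of 30 is 3.3% to 10% of the cohort, but those subjects contribute data until they leave. With one removal, the largest loss in percent with bleeding across the scenarios run is about 1.6 points.
- **That deleting the bullet would be enough.** The list is open-ended, and physician withdrawal allows the same removal. What is missing is a data-collection rule for any discontinuation without withdrawal of consent.

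**Conclusion.** The gap is real and modest. As written, the plan can lose non-fatal events in consenting subjects still on HM3 support, and nothing later in either document restores them.

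One effect needs no assumption about relative risk: the percent of patients with adverse events is understated. The loss is 3.0 points for bleeding and 0.7 for stroke if 3 of 30 leave at month 6. Across all the assumed scenarios, the bleeding loss runs from 0.6 points (1 of 30 at month 12, equal risk) to 7.8 points (5 of 30 at month 6, three times the hazard). Bias in the Kaplan-Meier and patient-year estimates is conditional on a risk difference and is zero without one. The 7.8-point end of the range also rests on that condition.

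The number, timing and risk of such discontinuations are assumptions, since the documents give none. The study is unpowered and has no success criterion (SAP 1.4.3 and 2.6), so no decision rule is affected. The case for acting is that the data loss is avoidable and cheap to prevent.

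**What to change.** This is a change to data collection and analysis only.

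1. In Protocol 5.5, remove non-compliance with the plan as a reason to end data collection.
2. Add a rule for every discontinuation without withdrawal of consent, whatever its reason: outcomes, adverse events, rehospitalizations and reoperations continue to be collected from site records until Month 24 or an outcome. Because 5.5 counts withdrawal as an outcome, say that here the outcome means death, transplant, explant, exchange or withdrawal of consent. Align 7.3.1.
3. In Protocol 8.2.1 and SAP 2.2.3 and 2.2.4, include these data in the primary analyses, and do not censor at a discontinuation that is not a withdrawal of consent.
4. Report discontinuations by reason. Sites already have to notify the sponsor of the reasons.

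The cost is a few sentences in each document and some extra chart review at about four sites for about 30 subjects.
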